Young people should never use nicotine in any form. While there is some evidence that e-cigarettes are less harmful than traditional cigarettes, they are not harmless and early exposure to nicotine can have long-lasting adverse effects. The majority of e-cigarettes contain nicotine, which has known health effects on brain development which occurs into the mid-20s. Specific risks include nicotine addiction, mood disorders, permanent lowering of impulse control, as well as negative impacts on attention and learning. The aerosol produced by e-cigarettes contains cancer-causing chemicals and tiny particles that reach deep into the lungs. E-cigarettes have also produced unintended injuries such as fires and explosions from defective batteries and poisonings from acute nicotine exposure through e-cigarette liquids. Finally, there is strong evidence that e-cigarette use can lead to the use of other tobacco products such as cigarettes. Reversing the dramatic gains over the past decade in reducing cigarette smoking among young people would be nothing short of a public health tragedy.

In response to this epidemic and given no available quitting resources for young people (cessation resources such as medication have no demonstrated effectiveness for young people^{6,7}), Truth Initiative launched a first-of-its kind e-cigarette cessation program designed specifically for young people in January 2019. The program is called *This is Quitting* and it is delivered entirely via text message. Mobile phone ownership is ubiquitous among young people and text messaging is a preferred communication modality in this age group. Text messaging is also easy to use, discreet, anonymous, and there is strong evidence supporting its effectiveness as a cessation intervention modality.⁸ *This is Quitting* was developed using best practices from smoking cessation research with young people, our extensive experience delivering digital tobacco cessation interventions to people of all ages, as well as formative research with young e-cigarette users and quitters.

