Young people enroll by texting "DITCHVAPE" to a short code and responding to the initial message with their age and first name (used for tailoring the program). Terms of Service and Privacy Policy are provided via a link in a text message. Users receive one age-appropriate message per day tailored to their enrollment date or quit date, which can be set and reset via text message. Those not ready to quit receive 4 weeks of messages focused on building skills and confidence. Those who set a quit date receive messages for a week before and 8 weeks afterward that include encouragement and support, skill- and self-efficacy building exercises, coping strategies, and information about the risks of vaping, benefits of quitting, and cutting down to quit. Keywords COPE, STRESS, SLIP, and MORE provide on-demand support. Sample text messages can be found at the end of this protocol. Users can unsubscribe by texting STOP. E-cigarette use and abstinence are assessed via text message at 14, 30, 60, and 90 days following an enrollee's quit date or enrollment date. At 14 days, enrollees are asked, "Have you cut down how much you vape in the past 2 weeks? Respond w/letter: A=I still vape the same amount, B=I vape less, C=I don't JUUL at all anymore." At 30, 60, and 90 days, enrollees are asked, "When was the last time you vaped, even a puff of someone else's? Respond w/ letter: A: in the past 7 days, B: 8–30 days ago, C: More than 30 days ago."

As of July 27, 2021, over 350,000 young people have enrolled, including over 130,000 adolescents aged 13-17, demonstrating the appeal of this treatment approach and the urgent need for quit vaping resources

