The scientific, clinical, and public health communities are desperate for proven, evidence-based cessation resources to address the vaping epidemic among young people. We are uniquely positioned to address this urgent need given our extensive experience in conducting large-scale, rigorous research trials of digital tobacco cessation interventions and our expertise in working with young people. We plan to rapidly disseminate study results to benefit other researchers/service providers and use these results to further enhance the program.

METHODS

Subjects

We will randomize 1800 e-cigarette users aged 13-17 years old who are interested in quitting in the next 30 days to the two main intervention arms (900/arm). We will aim to randomize 450 to the waitlist control arm. Other eligibility criteria include past 30-day e-cigarette use and US residence. To fully enroll in the study, individuals must text a study-specific phone number and respond to the system-generated message.

Recruitment and Enrollment

Potential participants will respond to online ads on various social media platforms (Facebook, Instagram, etc.) if they are current e-cigarette users who are interested in quitting and willing to participate in a research study. Clicking on the ad will lead them to a webpage that provides details about what participation in the study entails and describes incentives for participation. Those who are interested will complete an eligibility screener followed by informed consent and a baseline assessment. Those who complete the baseline will be randomized into one of three arms (see below for additional details) and instructed to text a specific keyword corresponding to their treatment assignment to the same phone number. Only those who respond to the first message from the text message program within 24 hours will be fully enrolled into the study. This requirement will be made explicit.

Randomization

Randomization occurs after completion of the online enrollment process (completed baseline survey). A computer algorithm that is part of the survey software will automate random allocation.

Interventions

This is Quitting: Participants will be enrolled to receive messages from This is Quitting as described above.

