Assessment-only control: After an initial enrollment message, participants will be contacted monthly to assess e-cigarette use. At the end of the study, participants will receive information about how to sign up for This is Quitting if they are interested.

Waitlist control: After an initial enrollment message, participants will only be contacted at 1 and 7 months to complete the follow-up assessments; there will be no other contact via text message. At the end of the study, participants will receive information about how to sign up for This is Quitting if they are interested.

Potential Problems and Solutions

Loss to follow-up is the primary concern in trials involving digital interventions, especially ones that employ an assessment only or minimal contact controls. For the treatment and assessment only control arms, we expect at least 75% follow-up at 1-month and 65% at 7-months based on our previous and ongoing digital mobile-based evaluations. If follow-up rates are lower than expected early in the trial, we will consider shortening the 7-month follow-up to gather only abstinence outcomes.

To maximize follow up rates we will:

- 1) provide clear information about the study at the outset, including expectations for follow-up;
- 2) reimburse participants up to \$30 per follow-up assessment;
- 3) collect interim abstinence assessments via text ("Retention Messages": \$5 incentive for each response) for intervention and assessment-only control arms;
- 4) send reminders about follow-up surveys via email and text messages;
- 5) conduct phone follow-ups for those unreachable by email and text messages;
- 6) contact participants via social media private messaging function (if permission given); and,
- 7) emphasize the importance of survey completion regardless of abstinence status.

Conducting research online involving incentives carries the potential for fraud and participant deception as there are often no direct interactions with the participants.¹¹ To prevent fraudulent enrollments and participation from bots, we will utilize the following features on the Qualtrics survey platform:

- 1) Prevent multiple submission: Enabling this option allows Qualtrics to place a cookie on the browser the first time someone takes the survey. The user will be flagged as duplicate if they come back to take the survey from the same browser and device without having cleared their cookies.

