- 2) Bot detection: Enabling bot detection flags responses that are likely completed by bots by assigning a score to each response. This feature uses Google's invisible reCaptcha technology to assign a score to each response, with a score of less than 0.5 meaning that the respondent is likely a bot.
- 3) Relevant ID: This feature analyzes a user's browser, operating system, and location to calculate a fraud score that indicates whether the respondent is attempting to take the survey multiple times.

We also require a valid email address for completion of the baseline survey (users must click on a survey link in their email to launch the baseline and complete enrollment), which has been shown to prevent bots. ¹² We will monitor emails and phone numbers used to enroll in the study on a daily basis and exclude any duplicates. We anticipate these measures will prevent the majority of any potentially fraudulent enrollments.

Measures

All randomized participants in both arms will be asked to complete all assessments. Assessments will occur at baseline and 1 month and 7 months post-randomization. The baseline survey will be conducted online and hosted on a secure server. Mixed-mode follow-up (email, phone, text) will be employed. Telephone surveys will be conducted by research staff blind to treatment. Text messages have demonstrated moderately high reliability (k=.66) compared with web-based surveys in assessing smoking outcomes¹³ and will be used as a final means of gathering abstinence data from non-responders. Most measures listed below are standard instruments used in cessation studies, and are reliable when administered via the Internet. ^{14,15}

Screening Variables. Individuals located outside the U.S. (as determined by IP address captured by the survey platform) will be ineligible to participate. To characterize the sample of users interested in the study and assess study eligibility, we will gather: demographics (age, education, income level, sexual and gender identity, race, and ethnicity); current e-cigarette use (use of e-cigarette containing nicotine or THC in the past 30 days)¹⁶; interest in quitting; contact information (e-mail and phone number to send baseline survey to and link text message sign-up data). These questions are being asked during screening so we can determine whether enrolled participants are representative of the wider population of e-cigarette users.

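### The tested program is open to the public, but the plan does not screen for its use or prespecify any measure of control-arm use, so dilution toward no difference would go unreported

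*Combined protocol and SAP*

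**What the plan says.** The introduction describes a service already in operation: "Truth Initiative launched a first-of-its kind e-cigarette cessation program designed specifically for young people in January 2019". A young person joins by texting a keyword "to a short code and responding to the initial message with their age and first name". On uptake it reports: "As of July 27, 2021, over 350,000 young people have enrolled, including over 130,000 adolescents aged 13-17".

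Under Methods, Subjects, participants must be 13-17 and interested in quitting within 30 days. The section then adds: "Other eligibility criteria include past 30-day e-cigarette use and US residence". The Screening Variables paragraph lists demographics, current e-cigarette use, interest in quitting and contact details. Neither place mentions use of the program.

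For each control arm, Methods, Interventions says: "At the end of the study, participants will receive information about how to sign up for This is Quitting if they are interested". Nothing in the document addresses sign-up before then.

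The one stated check on phone numbers, under Potential Problems and Solutions, is: "We will monitor emails and phone numbers used to enroll in the study on a daily basis and exclude any duplicates". It looks for repeats within the study and does not compare numbers with the public program's enrollees.

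Baseline Variables includes a general quitting history. Mediating Variables covers engagement data such as keyword use, days enrolled and messages received, collected to test mediation of the treatment effect. Outcome Measures and the Data Analysis Plan contain no item on use of the program by controls and no contamination analysis.

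**The concern.** The primary comparison assumes that one arm gets the program and the other does not. Two routes can erode that. Some participants in any arm may already be enrolled in the public program when randomized, so assignment changes little for them. Some controls, all of whom want to quit within 30 days, may find and join the program during the 7-month follow-up.

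Both routes shrink the observed difference. If the result is small or null, a reader will want to know whether the program is weak or the comparison was diluted, and the planned reporting gives no figure to help. The waitlist arm does not settle this, because its members have the same open access. The sponsor added that arm because abstinence among assessment-only controls in the young adult trial was relatively high. Outside use of the program is one possible contributor to such rates, so the gap touches a question the sponsor itself raises.

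**Working it through.** **Inputs from the protocol**
- 900 per main arm (Methods, Subjects).
- Abstinence of 24.1% (program) and 18.6% (assessment-only), with missing counted as vaping, from the earlier young adult trial (introduction).

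**Assumptions, not in the protocol**
- Two-sided alpha of 0.05.
- The young adult rates apply to adolescents.
- A share *c* of controls uses the program, beyond any such use already contained in the 18.6%.
- Each such control gains a fraction *b* of the benefit.

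**Baseline.** The protocol gives no derivation of 900 per arm, so there is no stated power to reproduce. With p1 = 0.241, p0 = 0.186 and p̄ = (p1 + p0)/2 = 0.2135:

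Power = Φ{ [ (p1 − p0) − 1.96·√(2p̄(1−p̄)/n) ] / √( [p1(1−p1) + p0(1−p0)]/n ) }

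= Φ{ [0.055 − 1.96 × 0.01932] / 0.01927 } = Φ(0.889) = 81.3%.

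Under the same assumptions 80% power needs 871 per arm. So 900 fits an 80% target at the young adult effect, although the protocol does not say that this was the basis.

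**Controls who use the program.** The control rate becomes 0.186 + *c*·*b*·0.055. For *c* = 10% and *b* = 1 it is 0.1915. The difference is 0.0495 and power is Φ{ [0.0495 − 1.96 × 0.01941] / 0.01937 } = 72.3%. The full range:

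| Share of controls | Difference, full benefit (points) | Power, full benefit | Power, half benefit |
|---|---|---|---|
| 0% | 5.5 | 81.3% | 81.3% |
| 2% | 5.4 | 79.7% | 80.5% |
| 5% | 5.2 | 77.0% | 79.2% |
| 10% | 4.95 | 72.3% | 77.0% |
| 20% | 4.4 | 61.7% | 72.3% |

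Half benefit at 10% equals full benefit at 5%, because only the product *c*·*b* enters the formula.

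**Users at entry.** Suppose a share *u* of both arms already uses the program, gains nothing further from assignment, and otherwise stays at 18.6%. The program-arm rate becomes 0.186 + 0.055·(1 − *u*). At *u* = 5%, 10% and 20% the difference is again 5.2, 4.95 and 4.4 points, and power is 77.4%, 73.1% and 63.3%. This is close to the full-benefit column but not identical.

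**The case against.** Much of the concern rests on silence. The eligibility sentence is not a closed list, the survey instruments are not reproduced, and the quitting-history item could ask about the program. The engagement extraction is not restricted in words to one arm. This stands as a limit: what can be said is that no screening for program use and no control-arm match is stated.

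The sizes lean toward the upper end. Full benefit in every crossover is generous. The 18.6% comes from a trial of the same program and may already include outside use. The protocol never says that 900 was sized on these rates. These points stand, and they are why half benefit is shown and the shares are read as contamination beyond the earlier trial's level.

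A reader might infer more than the document supports:
- *That contamination is known to be substantial.* The figure of 130,000 is cumulative from January 2019. It has no denominator and includes people who stopped or have since turned 18. It shows that access is real and gives no rate.
- *That consent hands controls the program.* Consent describes each study condition, but the protocol does not say that it gives the public keyword.
- *That the trial could never separate a weak program from a diluted comparison.* Participants' phone numbers are collected and accessible to staff, so a match could still be run after the trial. The defect is that none is prespecified.
- *That every past user should be excluded by a number match before randomization.* Screening (Step 2) comes before consent (Step 4) and enrollment is fully automated, so such a match does not fit the described flow. Admitting past users who still vape is a defensible choice in a trial framed as comparative effectiveness.

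The dilution runs toward no difference, so it would not by itself produce a false positive.

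**Conclusion.** The concern holds as a gap in screening, measurement and reporting. The program is open to the age group under study, the stated criteria and screening variables do not address its use, and no measure or analysis of control-arm use is prespecified. Any dilution would be toward no difference and would go unreported under the plan as written.

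Its size cannot be derived from the protocol. On the stated assumptions there is little slack: about 2% of controls with full benefit brings power just below 80%, and 20% costs roughly 20 percentage points with full benefit or 9 with half. These figures show sensitivity and are not a forecast. The change is worth making because it is cheap and the result would be hard to interpret without it.

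**What to change.** 1. Add a question on current and past use of This is Quitting to the eligibility screener. Treat current enrollees as ineligible. Record past use as a baseline variable and do not exclude all past users. A question fits the existing automated flow.
2. Prespecify a match of participants' phone numbers to the program's enrollment records at the 7-month data lock, with a line in the consent text to cover it. Report prior use by arm, and crossover separately for the assessment-only and waitlist arms.
3. Keep the intention-to-treat comparison primary. Add a complier-average (instrumental-variable) estimate as a prespecified secondary analysis, with its assumptions stated.

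Cost: one screener item, a consent line, a database match and a few sentences in the analysis plan. Some screened users become ineligible. Self-report will miss some users, and the match will miss anyone who joined under another number. The match also depends on the sponsor holding subscriber numbers, which is inferred from its running the text service, and on privacy terms that are not in the document and should be checked first.

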among young people. Preliminary evaluation data collected among an initial cohort of roughly 27,000 users has shown high levels of engagement in the program and high rates of abstinence among responders. Roughly ¾ of users set a quit date, with the most common quit date being the day of enrollment. Interactive keywords were used by 45.5% of teens and 38.4% of YA. Response rates to follow-up assessment questions were 36.9% at 14 days and 21.0% at 90 days. At 14 days, 60.8% of respondents indicated they had reduced or stopped using e-cigarettes altogether. At 90 days, 7-day point prevalence abstinence (ppa) was 25% and 30-day ppa was 16%. The high volume of enrollment in a short period of time, high levels of engagement with the program, and e-cigarette reduction and cessation results demonstrate that young people are interested in quitting vaping and can be engaged in an easily accessible, anonymous digital platform.

We recently completed an evaluation of This is Quitting with 2,588 young adults aged 18-24. Under an intention-to-treat analysis with missingness coded as vaping, abstinence rates were 24.1% among participants assigned to the intervention (This is Quitting) and 18.6% among participants in the assessment only control arm, a statistically significant difference (Odds Ratio=1.39, 95% CI 1.15-1.68, p< 0.001). [10]

Building on previous research, the primary aim of the current study is to conduct a comparative effectiveness trial to evaluate the effectiveness of *This is Quitting* in promoting abstinence from e-cigarettes among adolescents aged 13-17. This study is a 2-arm randomized controlled trial conducted among young users aged 13-17 recruited through online channels. Participants will be randomized to *This is Quitting* or an assessment-only control condition and followed for 7 months to roughly correspond to 6-months post-treatment. The secondary aim is to examine potential mediators of program effectiveness, including treatment engagement and changes in self-efficacy and perceived social support for quitting.

We will also include a waitlist control arm to evaluate the influence of assessment reactivity and retention incentives given relatively high quit rates among assessment-only control participants in the previous YA trial and the dearth of data on adolescent vaping cessation. This arm was not included in sample size calculations.

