Baseline Variables. To characterize the sample and explore potential moderators of treatment effectiveness, we will gather: additional demographics (student status, employment status); current ecigarette use and history (frequency and rate, 16,17 age of first use, motivation to quit and quitting history 18); nicotine dependence will be assessed with the Penn State Electronic Cigarette Dependence Index 19, EDS/PROMISE-E, 20 the Hooked on Nicotine Checklist, 21 and the E-cigarette Fagerström Test of Cigarette Dependence (e-FTCD) 22; other substance use (other tobacco products, alcohol) and mental health symptoms 23; and adverse childhood events. 24,25 For co-morbidities and adverse childhood events, we chose measures that are validated for use among adolescents. In order to minimize risk to participants, we deliberately avoided measures or deleted questions that assessed sensitive topics such as suicidality. Given evolving trends of e-cigarette use and perception, we will also ask about perception about harm from e-cigarettes, reasons for wanting to quit, and reasons for joining the study. To account for potential predictors of dropout, we will ask about motivation to use or quit e-cigarettes and potential barriers to quitting (e.g., social influences). We will assess baseline levels of perceived level of social support, 26,27 perceived social norms, and perceived self-efficacy for quitting and examine changes in these variables as potential mediators of treatment effectiveness.

Mediating Variables. We hypothesize that treatment engagement will mediate the relationship between treatment assignment and abstinence outcomes. We will extract data regarding replies to interactive text messages (e.g., setting a quit date, keyword use) as well as unsubscribe status, number of days enrolled, and total number of messages received. All text message interactions are date/time stamped.

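### The four-step mediation rule requires a significant total effect that an indirect effect does not need and an attenuation test that the text does not define, and the engagement hypothesis has no mediation analysis

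*Combined protocol and SAP*

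**What the plan says.** The background section of the combined protocol and SAP sets the aim: "The secondary aim is to examine potential mediators of program effectiveness, including treatment engagement and changes in self-efficacy and perceived social support for quitting". Under Measures, Mediating Variables, it adds: "We hypothesize that treatment engagement will mediate the relationship between treatment assignment and abstinence outcomes". The engagement data listed there are interactive replies (such as quit-date setting and keyword use), unsubscribe status, days enrolled and messages received.

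The Mediator Analysis section models only perceived social support and perceived self-efficacy. With X as treatment, Z as the mediator and Y as abstinence, it requires (1) a significant X–Z effect, A; (2) a significant Z–Y effect, B; (3) a significant X–Y effect, C; and (4) a significant weakening of C once the other paths are in the model. It names no test, scale or interval method. It refers to Figure 1, which is not reproduced in the available text. Engagement appears in the Data Analysis Plan only among the outcomes under Secondary Analyses.

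The mediators are timed at 1 and 7 months post-treatment in this section, but the assessments are timed post-randomization under Measures.

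Text contact differs by arm. In the program, "Users receive one age-appropriate message per day tailored to their enrollment date or quit date", and "Those who set a quit date receive messages for a week before and 8 weeks afterward"; those not ready to quit get 4 weeks of messages. In the assessment-only arm, "After an initial enrollment message, participants will be contacted monthly to assess e-cigarette use". In the waitlist arm, apart from the enrollment message and the two follow-ups, "there will be no other contact via text message". Payment for participation gives 7 paid text assessments to both the intervention and assessment-only arms.

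**The concern.** An indirect effect is the product of what treatment does to the mediator and what the mediator does to the outcome. It can be real and well estimated when the total effect misses significance. Condition 3 therefore limits the chance of a positive mediation finding to the power of the main comparison, however strong the mediator is.

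Condition 4 cannot be carried out from the text alone. One natural reading compares the treatment coefficient in two logistic models. Logistic coefficients change when a predictor of the outcome is added even if nothing is mediated, so that comparison mixes mediation with rescaling.

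For engagement, the hypothesis and the analysis do not meet. A stated part of the secondary aim has no stated mediation method, and the X–Z–Y model would tell little about it because several of the measures are largely fixed by assignment.

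**Working it through.** **Inputs.** From the documents: 900 per main arm (Subjects); abstinence of 24.1% vs 18.6% in the young-adult trial (background); 75% expected follow-up at 1 month (Potential Problems and Solutions). Assumed: two-sided 5% level, young-adult rates carried over to adolescents, and all mediator strengths. No alpha, power or target effect is given for 900 per arm, so that figure cannot be reproduced.

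**Check of the prior result.** OR = (0.241/0.759)/(0.186/0.814) = 1.39. With 2,588/2 = 1,294 per arm (assumed equal split), the Wald 95% interval is 1.15 to 1.68, as the protocol states.

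**Condition 3.** C = ln(1.39) = 0.329. At 900 per arm, SE = √(1/216.9 + 1/683.1 + 1/167.4 + 1/732.6) = 0.116. Power = Φ(0.329/0.116 − 1.96) = Φ(0.88) = 81.1%, so the condition fails in about 19% of trials. By the pooled two-proportion formula (81.3% at the same rates), power is 61% at OR 1.3 and 34% at OR 1.2 with an 18.6% control rate.

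**Condition 4 on the logit scale.** Model: Z given X is normal with mean aX and SD 1; logit P(Y) = b0 + C′X + bZ; marginal rates held at 18.6% and 24.1%. The true share is the natural indirect effect divided by the 5.5-point risk difference. The apparent share is (C − C′)/C.

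| a (SD) | b (log-OR per SD) | C′ | True share | Apparent share |
|---|---|---|---|---|
| 0.185 | 0.25 | 0.286 | 15% | 0.043/0.329 = 13% |
| 0.095 | 0.5 | 0.295 | 15% | 0.034/0.329 = 10% |
| 0.097 | 1.0 | 0.284 | 27% | 0.045/0.329 = 13.5% |

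With no mediation at all (a = 0, b = 1.0), C moves from 0.329 to 0.381 when the mediator is added. That change is rescaling alone.

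**Whole rule, same three cases, 900 per arm, complete mediator data.**

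| Criterion | Case 1 | Case 2 | Case 3 |
|---|---|---|---|
| Four conditions, product-of-coefficients test | 75% | 42% | 49% |
| Four conditions, logit-difference test | 73% | 23% | 13.5% |
| Interval for a×b | 97% | 53% | 56% |
| Interval for a×b plus condition 3 | 79% | 44% | 50% |
| Risk-scale bootstrap interval (the proposed method) | 97% | 49% | 50% |

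The first four rows use 2,000 trials per case and the last uses 300 (400 bootstraps each), so the last row carries a simulation error of about √(0.5×0.5/300) = 3 points near 50%. A paired run of 400 trials per case gave 96%, 49% and 54% for the bootstrap against 75%, 41% and 47% for the four conditions with a product test: gaps of 21, 8 and 7 points. Coverage of the bootstrap interval was 96%, 94% and 96%. Condition 3 alone costs 97 − 79 = 18, 53 − 44 = 9 and 56 − 50 = 6 points from the rounded rows.

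**With 1-month loss.** 900 × 0.75 = 675 per arm. Month-7 rates among 1-month responders are not given; taking them between 18.6%/24.1% and those rates divided by 0.75 (24.8%/32.1%), the four conditions with a product test succeed in 55–76%, 29–44% and 34–47%, against 87–95%, 41–51% and 43–51% for the a×b interval.

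**Engagement.** Program messages number about 4×7 = 28, or 8×7 = 56 to 9×7 = 63 after a quit date is set, before keywords, resets or stopping. The assessment-only arm's 7 text assessments are also sent to the intervention arm. Quit-date setting and keyword use have no stated counterpart in either control arm. Path A is thus largely fixed by design, and path B compares people who chose to engage with people who did not. The adjustment under Primary Analysis is for the intervention-outcome relationship; path B needs mediator-outcome confounders.

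**The case against.** The best defence is that condition 3 is a deliberate, conservative gate: the plan asks whether the treatment effect is mediated, so it first asks for an effect. The gate can also limit false claims. The young-adult and teen cohort set quit dates early, "with the most common quit date being the day of enrollment", so abstinence at 1 month could raise self-efficacy rather than follow from it. In simulations of that case (675 per arm), the a×b interval is positive in 3% to 65% of trials, against 0% to 43% for the four conditions with a product test. This cost is real and belongs with the fix. It does not rescue the gate: the error comes from confounding of mediator and outcome, which both methods share, and the gate masks it only by lowering power. Adjusting for 1-month abstinence brings the interval's false positives to 0.3% or less.

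Four stronger readings are tempting and not supported:

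- A reader might infer that the control arms can share no engagement measure. The assessment-only arm is texted monthly, so replies, unsubscribing, days enrolled and messages received can be recorded there.
- A reader might infer, from "Interactive keywords were used by 45.5% of teens and 38.4% of YA", that keyword use will be entered as a mediator and yield spurious mediation. The plan states no such analysis, so any figure for that bias prices a model nobody has specified.
- A reader might take 23% and 13.5% as the rule's performance. They hold only if condition 4 is a logit-difference test, which the odds wording and the logistic primary model suggest but do not state.
- A reader might infer that the open choices will be made after seeing the data. Figure 1 is not shown, and the Data and Safety Monitoring Board section allows for a separate final plan; either may settle them.

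**Conclusion.** The point stands for the secondary aim. Condition 3 is unnecessary and fails in about 19% of trials at 900 per arm if the young-adult rates apply; that figure needs only the sample size, the rates and a two-sided 5% level. The loss for the whole rule depends on assumed mediator strengths: about 21 points in one case and 7 to 8 in the other two under the product reading (paired run). Condition 4 lacks a test and scale in the text; read as a fall in the logit coefficient, it also understates the mediated share, slightly for a weak mediator and by half for the strongest one examined (13.5% against 27%).

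The missing engagement analysis, the choice between 1-month and 7-month change, and the two timing terms are mainly matters to clarify. The primary comparison is unaffected.

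**What to change.** - Replace the four-step rule with an estimated indirect effect on the risk scale and a bootstrap interval, adjusted for the baseline mediator and for baseline mediator-outcome confounders already collected (motivation, dependence). Report it as non-causal evidence.
- Use 1-month change as the main mediator, because month-7 change is concurrent with the outcome and the plan contemplates cutting that survey to abstinence only. Report month-7 change descriptively. State how missing 1-month scores are handled.
- Add a sensitivity analysis adjusted for 1-month abstinence, and read the two results together.
- Analyse program engagement within the intervention arm as an adjusted association with abstinence.
- Reconcile the post-treatment and post-randomization timing.

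**Cost.** SAP wording and standard software; no new data. Gains after 1 month are missed, although messages run for 8 weeks after the quit date. Power for small indirect effects stays limited, at about 49% in the second case. Where early abstinence itself raises self-efficacy, the interval is positive more often than the four-step rule. The sensitivity analysis guards against that at a price: in simulation, detection of a genuine effect fell from 54–70% to 2–3% when it ran wholly through early abstinence, and from 80–100% to 68–100% when self-efficacy also acted directly.
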